4.3 Study Design

This is a pilot, randomized controlled trial (n=240) to test the primary outcome of treatment acceptability and secondary outcomes of efficacy and mechanism of change for the Actify app vs. the active control app (the National Cancer Institute's QuitGuide app). We will test the interventions using an 8-week treatment period, and, consistent with the evaluation period in our previous cessation app pilot study, our primary outcomes will be assessed at the 8-week end-of-treatment mark. We will also collect 6-month follow-up data to assess long-term outcomes.

- 4.3.1 **Primary Endpoints:** Treatment acceptability as indicated by user satisfaction with assigned treatment (user satisfaction ratings of the assigned app at 8 weeks post-

randomization) and app utilization (total number of app server-recorded openings of the assigned intervention)

4.3.2 Secondary Endpoints: Treatment efficacy (smoking cessation) and changes to theory-based mechanisms of change (behavioral activation).

- Treatment efficacy:
 - Self-reported 30-day point prevalence abstinence (PPA) from smoking at 8 weeks post-randomization
 - Self-reported 30-day PPA from smoking at 6 months post-randomization; Biochemically-confirmed 30-day PPA from smoking at 8 weeks and 6 months post-randomization; Self-reported and biochemically confirmed 7-day PPA from smoking at 8 weeks and 6 months post-randomization; Self-reported and biochemically confirmed 30-day PPA from cigarettes and other non-medicinal nicotine/tobacco products at 8 weeks and 6 months, including e-cigarettes
- Mechanisms of change:
 - Change in behavioral activation from baseline to 8 weeks post-randomization
 - Change in depressive symptoms from baseline to 8 weeks post-randomization

4.3.3 Exploratory Endpoints: Differences in treatment effects by pre-quit depression (depressed vs. not depressed)

4.4 Estimated Accrual:

We estimate that our recruitment efforts will yield 904 screened, 490 eligible, 416 consented, and 240 randomized into the trial (120 per arm). We conservatively allotted 9 months for recruitment (26 enrolled/month).

4.5 Name of Sponsor/Funding Source:

National Institute on Drug Abuse, Grant Number: 1R34DA050967

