14.2 Primary/Secondary Endpoints/Hypotheses and Analytical Methods

Data analyses will be conducted using the intent-to-treat approach, except where otherwise indicated.

Aim 1. Conduct a pilot, randomized controlled trial (n=240) to test the primary outcome of treatment acceptability and secondary outcomes of efficacy and mechanism of change for the two treatment groups: Actify vs. QuitGuide.

ENDPOINTS

- The primary acceptability endpoints are number of app openings and overall satisfaction ratings.

- For smoking cessation:
 - The primary endpoint is the 30-day point prevalence abstinence (PPA) at 8 weeks post-randomization, which is comparable to the primary endpoints of the two extant trials of smartphone apps for smoking cessation [10, 34].
 - The secondary endpoints are 7- and 30-day PPA at 6 months, 7-day PPA at 8 weeks, and biochemically-confirmed abstinence from any nicotine/tobacco product (other than FDA-approved cessation medications) between baseline and 8-week and 6-month follow-ups.
- For mechanism of change,
 - The primary endpoint is the change in BADS scores between baseline and the 8-week follow-up
 - The secondary endpoint is the change in depressive symptoms over the same time period.

ANALYTICAL METHODS

Linear regression will be used to evaluate treatment effects between the two arms for continuous endpoints. This model will adjust for any demographic or other variables that differ between study arms at baseline and are related to outcome as well as the stratification factors (depression severity, sex assigned at birth, and level of smoking). To compare binary endpoints between two arms (e.g. smoking abstinence), a logistic regression model will be conducted with control for potential confounding variables and the stratification variable. Sensitivity analyses excluding participants using concomitant treatment for smoking cessation and/or depression will also be conducted.

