Additional exploratory analyses will be conducted. To explore differential treatment effects by pre-quit depression, we will preliminarily test the interaction of treatment group assignment and pre-quit depression and present descriptive data on quit rates for the four subgroups (Actify, depressed; Actify non-depressed; QuitGuide, depressed; QuitGuide non-depressed). To evaluate the theory underlying BAT-D for smoking cessation, we will examine change in BADS scores between baseline and 8-week follow-up as a predictor of 30-day PPA at 6-month follow-up using a logistic regression model. To generate empirical evidence to set usage benchmarks for the Actify app, we will evaluate the relationship between app “dosage” and cessation outcomes by regressing 30-day PPA at 8 weeks on objective measures of app utilization (e.g., number of app logins, total duration of use) using logistic regression. Similar to our feature analysis of SmartQuit that guided future app development [69], we will also regress 30-day PPA at 8 weeks on utilization of specific app components (e.g., scheduling, mood tracking) to determine “active ingredients.” To evaluate the relationship between user characteristics and treatment utilization and outcomes, we will use logistic (for cessation outcomes) or negative binomial (for login count data) models and baseline data as predictors. To examine sex as a biological variable, we will preliminarily test for sex differences in treatment response by descriptively examining results separately by sex.

Missing data: Consistent with prevailing standards for smoking cessation trials [88], participants with missing smoking data will be considered non-abstinent in the primary analysis. As a sensitivity analysis, we will also report abstinence rates from complete case analyses and multiple imputation. Treatment acceptability and mechanism of change (i.e., behavioral activation [BADS] and depression [PHQ-8] scores) will be analyzed using complete case analysis.

Modified intent-to-treat approach. Because treatment acceptability is the primary outcome of this pilot trial, and because a valid assessment of acceptability is not possible in cases where there is pre-intervention attrition (i.e., never downloading or opening the assigned app), we will use a modified intent-to-treat approach in which only those participants who open their assigned app at least once will be included in the outcome analyses.

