3.3 Data analysis plan

Primary statistical review of the study will be conducted by the study statistician at the end of the study, guided by the Principal Investigator. (See section 7 for detailed analysis plan).

4 Quality assurance plan

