4.2.2 Procedures during data transmission

Forms used by participants and staff will be web-based forms. Data are maintained on a server in a locked server room at Fred Hutch. Full access to the server is restricted to two staff members of the Fred Hutch Public Health Sciences Information Technology (PHS-IT) group and the two developers of the study management system.

Project staff access the study database via the Study Management (SM) Web site. The SM Web site is only accessible from specific Internet Protocol (IP) addresses used by study staff. All communication with the SM Web site occurs over Secure Sockets Layer (SSL). Both intervention arms will store participant usage data.

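### Number of app openings, a co-primary endpoint, is analysed only in people with at least one opening (section 14.2), while DSMP 7.2 has no such restriction

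*Combined protocol and SAP*

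**What the plan says.** Section 14.2 begins from a general principle: "Data analyses will be conducted using the intent-to-treat approach, except where otherwise indicated". It then names the endpoints: "The primary acceptability endpoints are number of app openings and overall satisfaction ratings". Section 4.3.1 defines utilization as a server-recorded count. The synopsis and DSMP 1.2 call the same quantity log-ins, and DSMP 1.2 labels it co-primary.

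The modified intent-to-treat paragraph at the end of 14.2 then says that "only those participants who open their assigned app at least once will be included in the outcome analyses". Its reason is that "a valid assessment of acceptability is not possible in cases where there is pre-intervention attrition". Utilization is not exempted, and no all-randomized analysis of it is planned.

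DSMP 7.2 (Appendix A) repeats the intent-to-treat sentence and nearly all of the remaining 14.2 text, including the missing-data paragraph. It has no modified intent-to-treat paragraph and no minimum-use condition. DSMP 3.3 points to that part of the DSMP for the analysis: "See section 7 for detailed analysis plan".

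**The concern.** A participant's value on the utilization endpoint decides whether that value is analysed. For satisfaction, requiring an opening makes sense, because someone who never saw the app cannot rate it. For a count kept by the server, zero is an observation. DSMP 4.2.2 confirms that the data exist: "Both intervention arms will store participant usage data". Never opening the assigned app is also arguably the clearest sign of low utilization.

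The selection happens after randomization. Under 14.4 the download link is sent to people already randomized, and 8.2 plans a text reminder and then a staff call for those who have not opened the app. The opener-only comparison therefore loses the protection of randomization whenever uptake differs between arms.

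Section 14.3 says the pilot is to supply a preliminary effect size for the next trial. Under the 14.2 rule, an app that fewer assigned people ever open is not penalised for it. If the people lost would have been light users, that app even looks better used. Two analysts, one following 14.2 and the other DSMP 7.2, would report different results for the same co-primary endpoint.

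**Working it through.** **Plan's own figure.** 60 per arm per depression stratum × 2 arms × 2 strata = 240, or 120 per arm, as 14.3 states. The plan has no power, alpha or effect-size calculation to reproduce.

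**Identity.** Never-openers count as zero, so in each arm

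mean in all randomized = uptake × mean among openers.

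Hence the all-randomized ratio = opener-only ratio × (Actify uptake / QuitGuide uptake). This needs no distributional assumption.

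- Uptake 85% vs 95% (assumed), opener ratio 1.00: 1.00 × 0.85/0.95 = 0.89.
- Uptake 75% vs 95% (assumed), opener ratio 1.00: 1.00 × 0.75/0.95 = 0.79.
- Break-even at 85% vs 95%: an opener ratio of 0.95/0.85 = 1.12 corresponds to no difference per randomized participant.
- Sign reversal with non-openers a random subset: if would-be usage is 6% higher on Actify, openers show 1.06 and all randomized show 1.06 × 0.85/0.95 = 0.95.
- In openings, with opener means of 20 and 12 (the Actify and SmartQuit figures in 2.2.1.d, for illustration only, since no QuitGuide mean is given): openers differ by 8.0. With 15% and 5% never opening, all randomized differ by 20 × 0.85 − 12 × 0.95 = 5.6.

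**When non-openers are not a random subset.** This was simulated with 120 per arm, linear regression on arm and the three stratification factors, two-sided 0.05 (assumed), and 3,000 runs per case (Monte Carlo error about 0.4 points near 5% and 0.9 near 50%). Would-be counts are negative binomial given at least 1, with mean 12 (assumed from SmartQuit). Dispersion k comes from the Actify single-arm trial (mean 20, SD 16): 20²/(16² − 20) = 400/236 = 1.69, taken as 1.7. Assumed log-scale covariate effects are +0.15 for depressed (50%), −0.15 for male (25%) and +0.10 for 20 or more cigarettes per day (50%). Would-be usage is identical in both arms. Differences are Actify minus QuitGuide, in openings.

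| Uptake, Actify / QuitGuide | Non-openers are | Openers: ratio; difference; share of runs with p<0.05 | All randomized: ratio; difference |
|---|---|---|---|
| 85% / 95% | random | 1.00; −0.02; 4.8% | 0.89; −1.26 |
| 85% / 95% | from the lower half | 1.07; +0.92; 11.4% | 0.96; −0.50 |
| 85% / 95% | the lightest users | 1.09; +1.19; 18.0% | 0.98; −0.29 |
| 75% / 95% | random | 1.00; −0.03; 4.9% | 0.79; −2.51 |
| 75% / 95% | from the lower half | 1.16; +2.00; 28.5% | 0.91; −1.04 |
| 75% / 95% | the lightest users | 1.20; +2.55; 45.7% | 0.94; −0.69 |

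Reverse case, 95% / 85%: openers 0.91 to 1.00, all randomized 1.02 to 1.12. Equal uptake, 90% / 90%: both 1.00. With heavier skew (k=0.7, assumed), opener ratios are 1.00 to 1.10 at 85% / 95% and 1.00 to 1.23 at 75% / 95%, with p<0.05 in 4.9% to 13.4% and 5.0% to 34.5% of runs.

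**The two sections side by side.** Section 14.2 drops a participant with zero openings. DSMP 7.2 keeps that participant, because its complete-case rule for acceptability does not remove a recorded zero.

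**The case against.** The exclusion is disclosed and reasoned, and the intent-to-treat sentence allows exceptions, so 14.2 is consistent with itself. Use among people who start is a legitimate question, different from uptake and use combined. With random non-opening at 75% vs 95%, the all-randomized analysis reaches p<0.05 in about 49% of runs although would-be usage is identical. A zero may also reflect a technical failure, or an entrant whose suspected deception cannot be confirmed under Appendix B.

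There may be few non-openers, and they may be balanced. Section 6.0 describes the apps alike, 14.4 sends identical weekly reminders, and 8.2 plans outreach in both arms. Section 8.2 also places randomization after a first log-in. At 93% vs 96% the opener-only ratio is only 1.00 to 1.03 (p<0.05 in 5.0% to 7.7% of runs) against 0.97 to 1.00. Finally, the DSMP (1/25/2022) predates the protocol version (6/13/2022), and DSMP 3.3 gives it no precedence.

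What stands is that uptake is unknown, that the gap may be small, and that the larger rejection rates need both a wide gap and light-user non-opening. The rest does not remove the point. The link to the assigned app follows assignment and 14.2 itself foresees people who never open it, so the log-in clause in 8.2 cannot mean opening that app. A difference in uptake is a real difference between the arms on a utilization endpoint. A change of sign does not require light-user non-opening, as the 1.06 example shows. The DSMP is a current appendix, whatever its date.

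**Conclusion.** The concern holds on both counts. The opener-only rule conditions the utilization co-primary on its own value after randomization, for a reason that does not apply to a recorded count, and DSMP 7.2 does not contain the rule.

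The direction and size of any distortion cannot be known from the documents. The two analysis sets differ by exactly the uptake ratio: no difference in the ratio at equal uptake, about 11% at 85% vs 95%, and about 21% at 75% vs 95%. How far openers then favour the less-opened app depends on the assumed usage distribution and on which people fail to open. This should be corrected before analysis. It concerns a primary endpoint and the result can change sign, but the pilot claims no power and balanced uptake would leave the ratio unchanged.

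**What to change.** In both 14.2 and DSMP 7.2:

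- Analyse utilization in all randomized participants, after the Appendix B fraud exclusions, with zero for anyone who had not opened the assigned app by week 8.
- Section 14.2 says "Linear regression will be used to evaluate treatment effects between the two arms for continuous endpoints". State that this model, with its covariates, covers the count and estimates a difference in means.
- Report the share opening by arm, and keep the opener-only comparison as a supplementary analysis.
- Keep the opening requirement for satisfaction ratings.
- State the analysis set endpoint by endpoint, identically in both sections. The present rule covers all outcome analyses, so the set for abstinence and the mechanism measures also has to read the same in both.
- Use one term, log-in or opening, for the event and for the at-least-once condition.

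The cost is wording, since usage is already stored in both arms. If uptake is equal and unrelated to usage, counting zeros reduces power. With k=1.7 and an assumed usage ratio of 1.33, it falls from 73.3% to 69.6% at 95% uptake, from 72.1% to 64.3% at 90%, and from 65.2% to 52.7% at 80%. The opener-only result remains available alongside.

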14.3 Sample Size and Power

As a pilot treatment development project, this study is not powered to detect statistically significant differences by treatment group. However, we plan to compare the outcomes of the two interventions to obtain a preliminary estimate of effect size. We will use these pilot data to optimize the treatment and study design and to prepare for a rigorous test of the efficacy of Actify in a subsequent R01. We plan to accrue a total of 240 patients in the pilot RCT for a balanced design. The NIDA Stage Model of behavioral treatment development suggests that pilot treatment development trials should include approximately 15-30 participants per arm to test feasibility [61]. However, as demonstrated in a recent simulation focused on sample size for pilot studies [87], binary outcomes (e.g., smoking abstinence) require higher sample sizes for reasonable precision of the effect size estimate than do continuous outcomes. To be conservative, and in consideration of the higher recruitment capacity in remotely conducted studies involving standalone mHealth interventions, we chose to include 60 subjects per arm within each stratum (depressed vs. non-depressed), as a sample size of 60 is a point of diminishing returns in terms of precision of effect size estimates for binary outcomes [87]. Thus, each arm will have 120 participants, of which 60 will meet criteria for mild to moderate depression.

14.4 Randomization

Following completion of the baseline survey, the web-based program will randomize participants to receive either Actify or QuitGuide with a 1:1 allocation ratio. The randomization algorithm will be developed by the study biostatistician, with stratification by presence of mild to moderate depressive symptoms (PHQ-8 < 5 or PHQ-8 ≥ 5), sex assigned at birth (2 levels: male or female) and level of smoking (2 levels: 20 or more cigarettes per day vs. < 20). Randomized participants will be emailed a secured link to download their assigned app. All participants will be emailed identical once-weekly reminders to use their assigned intervention. Although we project, based on recent data from our trial of web-based interventions [8], that the vast majority (92%) of outcome assessments will be completed via web-based survey, any outcome evaluator who has direct contact with participants will be blinded to treatment group assignment.

14.5 Ethnic and Gender Distribution Chart: Projected Target Accrual

Planned						
Racial Categories	Ethnic Categories				Total	
	Not Hispanic or Latino		Hispanic or Latino			
	Female	Male	Female	Male		
American Indian/ Alaska Native		2	0	0	6	
Asian	4	2	0	0	6	

Native Hawaiian or Other Pacific Islander	2	0	0	0	2
Black or African American	17	8	2	0	27
White	139	47	12	4	202
More than One Race	10	2	0	0	12
Total	176	61	14	4	255

15.0 INVESTIGATOR OBLIGATIONS

The PI is responsible for the conduct of the clinical trial at the site and is responsible for personally overseeing the treatment of all study subjects. The PI must assure that all study site personnel, including sub-Investigators and other study staff members, adhere to the study protocol and to all applicable regulations and guidelines regarding clinical trials both during and after study completion.

All subjects are informed of the nature of the program, its possible hazards, and their right to withdraw at any time, and each subject signs a form indicating their consent to participate prior to receiving any study-related procedures.

17.0 APPENDICES

Appendix A: Data & Safety Monitoring Plan

Appendix B: Fraud Prevention Protocol for Pilot Trial

*Included in this protocol document for Scientific Review Committee, all other appendices will be provided for IRB submission

1.1 Brief description of the protocol

This study aims to inform the development of an app (Actify!) for smoking cessation that is grounded in behavioral activation therapy for depression (BAT-D). The primary aims are to (1) complete development of the new app by adding cessation content, improving the app structure, conducting a 1-week diary study to evaluate the app's usability, and refining the app, and (2) conduct a pilot, randomized controlled trial (n=240) to test the primary outcome of treatment acceptability and secondary outcomes of efficacy and mechanism of change for the Actify app vs. the active control app (the National Cancer Institute's QuitGuide app). We will test the interventions using an 8-week treatment period, and, consistent with the evaluation period in our previous cessation app pilot study, our primary outcomes will be assessed at the 8-week end-of-treatment mark. We will also collect 6-month follow-up data to assess long-term outcomes.

1.2 Primary and secondary outcome measures

Acceptability outcomes:

- Co-primary: User satisfaction ratings of the assigned app at 8 weeks post-randomization
- Co-primary: Total number of log-ins to the assigned app at 8 weeks post-randomization

Smoking abstinence outcomes

- Primary: Self-reported 30-day point prevalence abstinence (PPA) from smoking at 8 weeks post-randomization
- Secondary:
 - Self-reported 30-day PPA from smoking at 6 months post-randomization
 - Biochemically-confirmed 30-day PPA from smoking at 8 weeks and 6 months post-randomization
 - Self-reported and biochemically confirmed 7-day PPA from smoking at 8 weeks and 6 months post-randomization
 - Self-reported and biochemically confirmed 30-day PPA from cigarettes and other non-medicinal nicotine/tobacco products at 8 weeks and 6 months, including e-cigarettes

Mechanisms of change

- Co-primary: Change in behavioral activation from baseline to at 8 weeks post-randomization
- Co-primary: Change in depressive symptoms from baseline to 8 weeks post-randomization

1.3 Inclusion/exclusion criteria

Inclusion criteria:

- age 18 or older
- current smoker, averaging at least 5 cigarettes/day for the last 30 days
- interested in quitting smoking in the next 30 days
- experience downloading and using one or more apps on their smartphone
- either screens negative (PHQ-8 score 0-4) for depression (Phase I n=5, Phase II n=120) or screens positive for mild to moderate current depressive symptoms (PHQ-8 score 5-19; Phase I n=5, Phase II n=120)
- willing and able to complete all study activities and willing to receive study compensation by US mail
- comfortable reading and writing in English
- have a mobile data plan and/or access to WiFi to support the use of the Actify app

- reside in the US
- have a smartphone either an iPhone (running iOS version 11 or higher) or an Android phone (running version 5.0 or higher)

Exclusion criteria:

- currently receiving behavioral treatment for depression (e.g., psychotherapy)
- current use of a depression app
- severe depression (PHQ-8 ≥ 20)
- receiving other treatment for smoking cessation
- previous use of the QuitGuide program
- current or recent (within the past year) enrollment in a Fred Hutch smoking cessation study
- employees/family of investigator or study center
- member of the same household as another participant
- woman who is pregnant or breastfeeding, or planning to become pregnant
- currently incarcerated
- is ineligible per fraud prevention protocol

